14.3 Interim analysis

No interim analysis will be conducted.

15. Quality control and quality assurance

15.1 Monitoring

To ensure that the trial is conducted properly, the principal investigator shall regularly monitor how research is progressing and whether it is being conducted according to the relevant guidelines, regulations, and research protocol to ensure its reliability. A person shall be designated for this purpose by the principal investigator.

The person in charge of monitoring will refer to a checklist prepared in advance. After confirming matters related to the implementation status and reliability of the research by telephone, fax, e-mail, or direct inspection of the original materials at the medical institution, the results will be compiled into a monitoring report and communicated to the principal investigator.

The following items shall be checked during the monitoring process

1) Cases

Records concerning consent acquisition, eligibility, and adverse events of the participants, as well as consistency between the data in the case report form and the records in the source documents will be confirmed. The trial will be conducted in compliance with the research protocol and ethical guidelines.

2) Procedures

The monitoring personnel will confirm that all procedures comply with the requirements set by Ethics Committee, that reports on safety are appropriately filled in and adhered to, that the review status of these procedures, the drugs, and equipment used in the trial are appropriately managed and recorded, and that procedures are properly conducted in compliance with the research protocol.

The person in charge of monitoring will not be involved in the evaluation of this research or the preparation of case report forms. In addition, this person must not divulge any information obtained during monitoring, as well as the confidentiality, identity, and other personal identifiers pertaining to research participants.

15.2 Data management

The principal investigator will designate a data management officer, who shall lay out in advance a data management plan following the Standard Operating Procedures of the Clinical Research Support Center. During the trial, this person shall perform data management operations on the applied procedures. After completion of the study, a report on the status of data management operations is prepared and submitted to the responsible physician together with fixed research data. Original materials will be stored as described in detail in **20** (Preservation of records). The person in charge of data management will not be involved in the clinical evaluation of the study.

15.3 Auditing

No audit will be conducted for this research.

16. Consideration about human rights and safety/disadvantage of research participants

16.1 Consideration about human rights (protection of personal information)

When handling raw data or consent documents related to the implementation of research, sufficient consideration shall be given to protection of research participants' confidentiality. For case reports and other documents presented outside the hospital, identification codes should be used. When publishing the results of the research, information that can identify research participants will not be included. The information and data collected during this study will be anonymized by removing personal identifiers, such as names and initials, and replacing them with a new code so that individuals cannot be identified. Data will be stored in the laboratory of the principal investigator (A501, 618, Clinical Research Building, University of Tokyo Hospital) on a stand-alone computer with a password lock. Any printed materials should also be stored in a lockable locker in the principal investigator's laboratory. The anonymization correspondence table will not be used for the analysis itself but to change the code back to personal information and dispose of it, such as when a research participant withdraws consent.

Data on research participants obtained in the course of the present study will not be used for any purpose other than the purpose of this research.

16.2 Consideration of safety and disadvantage, and balance with benefit

Research participants will consume food and undergo a total of four medical examinations and tests. Although the direct benefits of the research participants' participation in this study are unknown, they will contribute to the generation of scientific evidence on the efficacy of NMN in humans. Given that the present trial involves intervention, the possibility of adverse health effects, although not highly likely, cannot be excluded. Therefore, a consultation service will be set up in case any abnormality is detected, and the conditions for discontinuation will be strictly defined to minimize health hazards caused by ingestion. In addition, personal information will be anonymized and protected with locks and passwords to prevent leakage.

17. Cost burden for research participants

All tests and other procedures carried out as part of this study will be performed as uninsured medical treatment and will be covered by research expenses. There is no cost burden for research participants.

18. Compensation for health damage and insurance coverage

18.1 Compensation for health damage

If a study participant suffers health hazards due to this study during the study period, or if a study participant sues for damages caused by this study, and if the study investigator determines that there is a causal relationship between the adverse event and the test food, compensation will be provided within the scope of PL insurance coverage for food testing.

18.2 Participation in compensation insurance

The principal investigator and sub-investigators will be covered by liability insurance.

19. Compliance with the Declaration of Helsinki, ICH-GCP, and ethical guidelines

This research will be conducted in compliance with the latest version of the Declaration of Helsinki and the Ethical Guidelines for Medical Research Involving Human participants.

20. Preservation of records

The information and data collected during this study will be stored in a stand-alone computer with a password lock in the principal investigator's laboratory (A501 and 618, Clinical Research Building, University of Tokyo Hospital) after removing personal identifiers, such as names, initials, and patient IDs, and creating an anonymized correspondence table with a new code so that individuals cannot be identified. Any printed materials should also be stored in a lockable locker in the principal investigator's laboratory. The anonymization correspondence table will not be used for the analysis itself, but to change the code back to personal information when necessary, such as when a research participant withdraws consent, and to dispose of the relevant person's information and data. Information pertaining to this trial will be kept for 5 years from completion of the study or 3 years from the final publication of the study results. The information will be then disposed of in an unrecoverable form by shredding the paper media or deleting the electronic files. After completion of the study, the company responsible for allocation should send the registration form to the principal investigator, and the registration form will be kept.

21. Registration of the research plan and publication of research results

The content of the study plan is registered in UMIN-CTR before the start of the study. The principal investigator and cooperating physician will publish the results in a scientific article as soon as possible after completion of the study.

22. Research Organization

(Name) (Position) (Institution) (Department)(Contact)

○[name], Assistant Professor, Department of Diabetes & Metabolic Diseases, Graduate School of Medicine, The University of Tokyo (Tokyo, Japan), [name]

[name], Graduate Student, Department of Diabetes & Metabolic Diseases, Graduate School of Medicine, The University of Tokyo (Tokyo, Japan), [name]

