8) Blood test 2: CRP, hormone tests (free testosterone, testosterone, DHEA-S, osteocalcin, pentosidine, and adiponectin), IL6, NAD metabolism-related metabolites (NAD, NMN, nicotinamide, NA, NR, NAR, NAMN, NAAD tryptophan, methyl nicotinamide, quinolinic acid, glutathione, AMP, ADP, and ATP). About 5 mL of whole blood is sent frozen to the Department of Metabolism and Nutrition, Graduate School of Medicine and Pharmaceutical Science for Research, Toyama University, for measurement using a mass spectrometer. After measurements, the sample will be destroyed and the data will be sent to the principal investigator.

9) 75g OGTT at 0 min, 30 min, 60 min, and 120 min; measuring blood glucose, insulin, serum-CPR.

10) FMD test.

11) Bone density test: performed using a bone densitometer.

12) Radiological examination: abdominal CT scan.

13) Questionnaire: common questionnaires about food attitude and anti-aging QOL, MMSE-J, and MoCA-J. *MMSE-J and MoCA-J are administered only at week 0 and week 12.

14) Diary: during the intake period, the participants' physical condition and dietary survey will be recorded daily in a designated diary.

On each visit, the patient will be asked to come to the hospital with a fasting breakfast and no test food intake to perform the test properly.

9. Discontinuation criteria

The following criteria will be considered grounds for discontinuing the research.

- 1) If the research participant declines to participate in the research or withdraws consent.
- 2) If the eligibility of the participant is found to be no longer valid after enrollment.
- 3) If it is difficult to continue the research due to adverse events.
- 4) If the entire study is discontinued.
- 5) If the physician deems it appropriate to discontinue the research for any other reason.

If the principal investigator and sub-investigators determine that it is impossible to continue the study for any reason, the date, reason, and course of discontinuation/withdrawal will be clearly stated in the medical record and case report, and necessary tests will be conducted at the time of discontinuation/withdrawal to evaluate efficacy and safety.

In the case of discontinuation due to an adverse event, treatment or follow-up observation should be conducted until the patient recovers as much as possible to the original state.

10. Handling in the case of an adverse event

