10.1 Actions to be taken in the case of an adverse event

When an adverse event is recognized, the principal investigator or sub-investigator shall immediately take appropriate measures and record the event in the medical record and case report form without any discrepancy. In addition, when food intake is discontinued or treatment for an adverse event becomes necessary, research participants should be informed.

To identify the food during an emergency evaluation, the principal investigator will ask the person in charge of allocation to disclose the results by opening the package for the case in question.

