10.2 Reporting of serious adverse events

If the principal investigator recognizes the occurrence of a serious adverse event, it should be promptly reported to the hospital through the Clinical Research Support Center, and the hospital director shall request the Ethics Committee to deliberate on whether or not to continue the trial. The principal investigator shall share information on the occurrence of the adverse event with the sub-investigators involved in the research.

A first report (emergency report) and a second report (detailed report) shall be made.

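### Sections 16.1 and 20 provide for disposing of a participant's research data on withdrawal of consent without exempting adverse events already collected, which conflicts in effect with section 9 and can thin the safety table in 14.2

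*Protocol*

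**What the plan says.** **Disposal.** Section 20 gives the linking table two uses: to restore identity when necessary, "such as when a research participant withdraws consent, and to dispose of the relevant" person's information and data. Section 16.1 says that the table is used "to change the code back to personal information and dispose of it, such as when a research participant withdraws consent". Neither section mentions data collected before the withdrawal, adverse events, or a request from the participant as a condition.

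**Discontinuation.** The first ground in section 9 is: "If the research participant declines to participate in the research or withdraws consent". For participants whom the investigators judge unable to continue, section 9 then requires that the date, "reason, and course of discontinuation/withdrawal will be clearly stated in the medical record and case report". It adds that "necessary tests will be conducted at the time of discontinuation/withdrawal to evaluate efficacy and safety".

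**Adverse events.** Section 10.1 tells the investigators to "record the event in the medical record and case report form without any discrepancy". For a serious event, section 10.2 says that "it should be promptly reported to the hospital through the Clinical Research Support Center". Section 14.2 plans an incidence rate with a 95% confidence interval for each adverse event. It does not say how a participant whose data have been disposed of is counted.

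**The concern.** An adverse-event table is only as complete as the data set behind it. If the coded records of people who withdraw consent are removed, a person who reacted and then withdrew leaves both the numerator and the denominator. The loss is then related to the outcome, and if the test food causes the reaction it is also related to the arm. In that case the NMN arm looks safer than it was.

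This matters more here than in many small trials. Section 6.5 states that there were no reports of NMN administration in humans, so the adverse-event counts are among the main results. Section 3.2 anticipates gastrointestinal symptoms, flushing and liver damage. The participants are healthy volunteers, and section 16.2 describes the direct benefit to them as unknown, so withdrawing consent is a plausible response to an unpleasant symptom. An analysis plan cannot repair the loss, because it can only work on data that still exist.

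**Working it through.** **Step 1: the provisions side by side.** The plan states no figure on this point, so there is none to reproduce.

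| Question | Section 9 | Sections 16.1 and 20 |
|---|---|---|
| Does it cover withdrawal of consent? | Yes, as ground 1 | Yes, as the named example |
| What happens to the research record? | Date, reason and course are entered in the case report; tests are done to evaluate efficacy and safety | The person's information and data are disposed of |
| Is there an exception for safety data? | Not addressed | None |

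Section 9 has data generated for evaluation. Sections 16.1 and 20 then provide for disposing of the same person's data. Both can be carried out in sequence, but the first then no longer serves its stated purpose within the trial. Section 20 also gives a general retention period (5 years from completion or 3 years from final publication) without saying how withdrawals fit into it.

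**Step 2: what lies inside and outside the disposal text.** The case report form is a research record and holds the adverse events that feed section 14.2, so it falls within the text. The medical record and the serious-event report to the hospital are not named. A non-serious event such as flushing would therefore survive in the medical record, but section 10 provides no separate report of it to the hospital.

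**Step 3: which discontinuations are affected.** Only ground 1 involves withdrawal of consent. Ground 3, difficulty in continuing because of adverse events, does not lead to disposal, and section 9 adds follow-up for it.

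**Step 4: size, by illustration.** From section 14.1: 21 participants per group and a predicted dropout of 5%. Expected dropouts are 0.05 × 42 = 2.1, about one per arm. How many would withdraw consent, and how many of those would have had a reaction, is not in the protocol and is assumed here.

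Exact (Clopper-Pearson) 95% limits for x events in n people:

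- lower = 0.025 quantile of Beta(x, n − x + 1), or 0 if x = 0
- upper = 0.975 quantile of Beta(x + 1, n − x); if x = 0 this equals 1 − 0.025^(1/n)

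| Assumed case in one arm | All data kept | Withdrawn people's data disposed of |
|---|---|---|
| One reactor, who withdraws consent | 1/21 = 4.8% (0.1 to 23.8%) | 0/20 = 0% (0 to 16.8%) |
| Two reactors, both withdraw consent | 2/21 = 9.5% (1.2 to 30.4%) | 0/19 = 0% (0 to 17.6%) |

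Check of two limits: 1 − 0.025^(1/20) = 0.168 and 1 − 0.025^(1/19) = 0.176. If nobody with an event withdraws consent, no event is lost, although the denominator still shrinks with each disposal.

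**The case against.** The strongest reply is that these sections describe what a linking table is for and are not an operating rule. Section 20 says the table is used when necessary, both sections are about privacy and record keeping, and in section 16.1 the thing disposed of may be only the personal information. That has some force for section 16.1. It has less for section 20, which names the person's information and data and gives withdrawal of consent as its example. The extent and timing of disposal are left open, and that is itself a reason to settle them.

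A reader might also infer three stronger things that the protocol does not support:

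- **That adverse events are erased altogether.** The disposal text does not reach the medical record or serious-event reports already sent. What can be lost is the coded research copy, and with it the entry in the incidence table.
- **That sections 9 and 20 contradict each other outright.** Section 9 requires recording and testing but does not expressly require that the results be kept after consent is withdrawn. Its wording covers five different grounds. The conflict is one of effect.
- **That the loss is irreversible by rule.** The wording about destroying records beyond recovery belongs to the end of the retention period, not to withdrawal of consent.

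It is also fair that a participant with a troublesome symptom can leave under ground 3 with the data intact, that the 5% is dropout from any cause, and that the two intervals in each row of the illustration overlap widely. Finally, deletion on withdrawal may be a deliberate choice in favour of participants' rights. The consent terms and the ethical guidelines that the protocol follows are not at hand, so this cannot be ruled out. A rule that keeps deletion available on request respects that choice.

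**Conclusion.** The point holds in this limited form. Sections 16.1 and 20 provide for disposing of research data on withdrawal of consent with no exception for safety data already collected. This conflicts in effect with section 9 and can remove events from the analysis promised in section 14.2. It is a flaw in a stated rule, not a detail left for the analysis plan.

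The bias is a risk and not a certainty. It arises only if someone with an adverse event withdraws consent, as opposed to stopping under ground 3, and only if the coded case-report data are then disposed of before analysis. The figures also assume that the person would otherwise have been counted, that is, that the exclusion for low intake in section 14.2 is not applied to the adverse-event table. Under those assumptions a single case is enough to turn an arm's observed incidence of 4.8% into 0% and lower the upper confidence limit from 23.8% to 16.8%. The number of such cases cannot be estimated from the protocol.

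**What to change.** Reconcile sections 9, 16.1 and 20:

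1. State that coded data collected up to the withdrawal of consent, at least the adverse events, are retained and analysed, and that they are deleted only if the participant expressly asks for this.
2. Report the number of deletion requests by arm alongside the adverse-event table, so that a reader can see how many people are missing from it.
3. State in section 9 whether the exit tests of someone who withdraws consent belong to the retained data.
4. Word the consent document to match.

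This changes text only and adds no visits or tests. The participant keeps the right to deletion. The cost is Ethics Committee approval of the revised protocol and consent wording, which section 24 requires for any change. The revision must also fit the consent terms and the applicable ethical guidelines, which could not be checked here.

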This research will be conducted under a joint research agreement with Mitsubishi Corporation Life Sciences Limited., with the provision of test foods and funding. Researchers will report to the principal investigator on the status of conflicts of interest related to the research, including personal earnings, for every fiscal year while the research is conducted and when new items are reported. The principal investigator shall submit a self-report on conflicts of interest after confirming that the status of such conflicts is appropriately described, and shall follow the instructions of the hospital director (based on the opinion of the Conflict of Interest Management Committee).

The ownership of intellectual property rights shall be determined in accordance with the agreement with Mitsubishi Corporation Life Sciences Limited. When Mitsubishi Corporation Life Sciences Limited. uses the name of the implementing medical institution or the researcher for publicity or advertisement of the product, the content and method of such use shall be discussed with the principal investigator in advance.

1) Conflict of Interest in Research Funding and Research Organization

This research will be conducted under a contract research agreement with Mitsubishi Corporation Life Sciences Limited., which will provide funding and test food supplements. Mitsubishi Corporation Life Sciences Limited. will provide information on the test food supplements, but will not be involved in the conduct, analysis, or reporting of the study.

2) Conflict of interest of the researcher

The principal investigator of this study has no conflicts of interest to disclose.

The principal investigator will continuously check (once a year) with the investigators to determine if any new conflicts of interest have arisen in the planning, implementation, or reporting of the research, and which may affect the results of the study or the interpretation of the results. The principal investigator will confirm that implementation of the research does not compromise the rights and interests of participants.

24. Changes to the research protocol

Any changes (revisions) to the research protocol, explanatory documents, or consent forms must be reported in advance to the hospital director and approved by the Ethics Committee.

25. References

